10.3.2. Definition of SAE

If an event is not an AE per definition above, then it cannot be an SAE even if serious conditions are met (eg, hospitalization for signs/symptoms of the disease under study, death due to progression of disease).

An SAE is defined as any untoward medical occurrence that, at any dose:
a. Results in death
b. Is life-threatening The term 'life-threatening' in the definition of 'serious' refers to an event in which the subject was at risk of death at the time of the event. It does not refer to an event, which hypothetically might have caused death, if it were more severe.
c. Requires inpatient hospitalization or prolongation of existing hospitalization In general, hospitalization signifies that the subject has been detained (usually involving at least an overnight stay) at the hospital or emergency ward for observation and/or treatment that would not have been appropriate in the physician's office or outpatient setting. Complications that occur during hospitalization are AEs. If a complication prolongs hospitalization or fulfills any other serious criteria, the event is serious. When in doubt as to whether "hospitalization" occurred or was necessary, the AE should be considered serious. Hospitalization for elective treatment of a pre-existing condition that did not worsen from baseline is not considered an AE.
d. Results in persistent disability/incapacity The term disability means a substantial disruption of a person's ability to conduct normal life functions. This definition is not intended to include experiences of relatively minor medical significance such as uncomplicated headache, nausea, vomiting, diarrhea, influenza, and accidental trauma (eg, sprained ankle) which may interfere with or prevent everyday life functions but do not constitute a substantial disruption.
e. Is a congenital anomaly/birth defect

An SAE is defined as any untoward medical occurrence that, at any dose:

f. Other situations:

Medical or scientific judgment should be exercised in deciding whether SAE reporting is appropriate in other situations such as important medical events that may not be immediately life-threatening or result in death or hospitalization but may jeopardize the subject or may require medical or surgical intervention to prevent one of the other outcomes listed in the above definition. These events should usually be considered serious.

Examples of such events include invasive or malignant cancers, intensive treatment in an emergency room or at home for allergic bronchospasm, blood dyscrasias or convulsions that do not result in hospitalization, or development of drug dependency or drug abuse.

10.3.3. Adverse Events of Interest

Liver disorder is considered a potential risk and will be closely monitored. As such, liver events have been deemed of interest in the GB001 program.

Adverse events of interest will include alanine aminotransferase increased, aspartate aminotransferase increased, blood bilirubin increased and/or associated preferred terms alone or associated with other conditions of concern, that result in temporary or permanent discontinuation of IP as defined in Appendix 6 (Section 10.6, Table 5) with the exception of events for which subjects cannot be monitored. Follow-up liver laboratory values (Table 3, Appendix 2 [Section 10.2]) and additional information to characterize the etiology of the event are mandatory and specified in Appendix 6 (Section 10.6).

10.3.4. Recording and Follow Up of Adverse Events and Serious Adverse Events

AE and SAE Recording

- When an AE/SAE occurs, it is the responsibility of the Investigator to review all documentation (eg, hospital progress notes, laboratory reports, and diagnostics reports) related to the event.
- The Investigator will then record all relevant AE/SAE/AE of Interest information in the eCRF.
- It is **not** acceptable for the Investigator to send photocopies of the subject's medical records to the Sponsor in lieu of completion of the AE/SAE eCRF page.
- There may be instances when copies of medical records for certain cases are requested by the Sponsor. In this case, all subject identifiers, with the exception of the subject number, will be redacted on the copies of the medical records before submission to the Sponsor.
- The Investigator will attempt to establish a diagnosis of the event based on signs, symptoms, and/or other clinical information. Whenever possible, the diagnosis (not the individual signs/symptoms) will be documented as the AE/SAE.

Assessment of Intensity

The Investigator will assess intensity for each AE and SAE reported during the study and assign it to 1 of the following categories:

- Mild: An event that is easily tolerated by the subject, causing minimal discomfort and not interfering with everyday activities.
- Moderate: An event that causes sufficient discomfort and interferes with normal everyday activities.
- Severe: An event that prevents normal everyday activities. An AE that is assessed as severe should not be confused with a SAE. Severe is a category utilized for rating the intensity of an event; and both AEs and SAEs can be assessed as severe.

An event is defined as 'serious' when it meets at least 1 of the predefined outcomes as described in the definition of an SAE, NOT when it is rated as severe.

Assessment of Causality

- The Investigator is obligated to assess the relationship between IP and each occurrence of each AE/SAE.
- **Related** – The AE is known to occur with the IP, there is a reasonable possibility that the IP caused the AE, or there is a temporal relationship between the IP and event. Reasonable possibility means that there is evidence to suggest a causal relationship between the IP and the AE.
- **Not Related** – There is not a reasonable possibility that the administration of the IP caused the event, there is no temporal relationship between the IP and event onset, or an alternate etiology has been established.
- The Investigator will use clinical judgment to determine the relationship.
- Alternative causes, such as underlying disease(s), concomitant therapy, and other risk factors, as well as the temporal relationship of the event to IP administration will be considered and investigated.
- The Investigator will also consult the Investigator’s Brochure (IB) and/or Product Information, for marketed products, in his/her assessment.
- For each AE/SAE, the Investigator **must** document in the medical notes that he/she has reviewed the AE/SAE and has provided an assessment of causality.
- There may be situations in which an SAE has occurred, and the Investigator has minimal information to include in the initial report to the Sponsor. However, **it is very important that the Investigator always assess causality for every event before the initial transmission of the SAE data to the Sponsor.**
- The Investigator may change his/her opinion of causality in light of follow-up information and send a SAE follow-up report with the updated causality assessment.
- The causality assessment is one of the criteria used when determining regulatory reporting requirements.

Follow-up of AEs and SAEs

- The Investigator is obligated to perform or arrange for the conduct of supplemental measurements and/or evaluations as medically indicated or as requested by the Sponsor to elucidate the nature and/or causality of the AE or SAE as fully as possible. This may include additional laboratory tests or investigations, histopathological examinations, or consultation with other health care professionals.
- If a subject dies during participation in the study or during a recognized follow-up period, the Investigator will provide the Sponsor with a copy of any post-mortem findings including histopathology.
- New or updated information will be recorded in the originally completed eCRF.
- The Investigator will submit any updated SAE data to the Sponsor within 24 hours of receipt of the information.

10.3.5. Reporting of SAEs

SAE Reporting to the Sponsor via an Electronic Data Collection Tool

- The mechanism for reporting an SAE to the Sponsor will be the electronic data capture system.
- If the electronic system is unavailable, then the site will contact the Medical Monitor in order to report the event and submit the paper SAE report form via the contacts below within 24 hours.
- The site will enter the SAE data into the electronic system as soon as it becomes available.
- After the study is completed at a given site, the electronic data collection tool will be taken off-line to prevent the entry of new data or changes to existing data.
- If a site receives a report of a new SAE from a study subject or receives updated data on a previously reported SAE after the electronic data collection tool has been taken off-line, then the site can report this information via contact to the Medical Monitor and submitting the paper SAE report form via the contacts below.
- Contacts for SAE reporting can be found in below.

Non-North America:
Use numbers and access codes specific to the country as provided by Sponsor.

Or if not available,

10.4. Appendix 4: Contraceptive Guidance and Collection of Pregnancy Information

Definitions

Woman of Childbearing Potential (WOCBP)

A woman is considered fertile following menarche and until becoming post-menopausal unless permanently sterile (see below).

If fertility is unclear (eg, amenorrhea in adolescents or athletes) and a menstrual cycle cannot be confirmed before first dose of IP, additional evaluation should be considered.

Women in the following categories are not considered WOCBP

1. Premenarchal
2. Premenopausal female with 1 of the following:
 - Documented hysterectomy
 - Documented bilateral salpingectomy
 - Documented bilateral oophorectomy

For individuals with permanent infertility due to an alternate medical cause other than the above, (eg, Mullerian agenesis, androgen insensitivity), Investigator discretion should be applied to determining study entry.

Note: Documentation can come from the site personnel's review of the subject's medical records, medical examination, or medical history interview.

3. Postmenopausal female
 - A postmenopausal state is defined as no menses for 12 months without an alternative medical cause.
 - A high follicle stimulating hormone (FSH) level in the postmenopausal range may be used to confirm a postmenopausal state in women not using hormonal contraception or hormonal replacement therapy (HRT). However, in the absence of 12 months of amenorrhea, confirmation with more than one FSH measurement is required.
 - Females on HRT and whose menopausal status is in doubt will be required to use one of the non-estrogen hormonal highly effective contraception methods if they wish to continue their HRT during the study. Otherwise, they must discontinue HRT to allow confirmation of postmenopausal status before study enrollment.

Contraception Guidance

Female Subjects:

- A female subject is eligible to participate if she is not pregnant or breastfeeding, and at least one of the following conditions applies:

- Is not a woman of childbearing potential (WOCBP)

OR

- Is a WOCBP and using a contraceptive method that is highly effective (with a failure rate of < 1% per year), preferably with low user dependency (see table below), at least 1 month prior to Screening, during the intervention period, and for 28 days after the last dose of IP, and agrees not to donate eggs (ova, oocytes) for the purpose of reproduction during this period. The Investigator should evaluate the effectiveness of the contraceptive method in relationship to the first dose of IP.
- A WOCBP must have a negative highly sensitive pregnancy test (urine or serum as required by local regulations) within 24 hours before the first dose of IP.
- If a urine test cannot be confirmed as negative (eg, an ambiguous result), a serum pregnancy test is required. In such cases, the subject must be excluded from participation if the serum pregnancy result is positive.

Contraceptive use by men or women should be consistent with local regulations regarding the use of contraceptive methods for those participating in clinical studies.

Highly Effective Methods^a That Have Low User Dependency

 • Implantable progestogen-only hormone contraception associated with inhibition of ovulation^b

 • Intrauterine device (IUD)

 • Intrauterine hormone-releasing system (IUS)^b

 • Bilateral tubal occlusion

 • Vasectomized partner (Vasectomized partner is a highly effective contraceptive method provided that the partner is the sole sexual partner of the woman of childbearing potential and the absence of sperm has been confirmed. If not, an additional highly effective method of contraception should be used. Spermatogenesis cycle is approximately 90 days.)
Highly Effective Methods^a That Are User Dependent

 • Combined (estrogen- and progestogen-containing) hormonal contraception associated with inhibition of ovulation 
 ○ oral ○ intravaginal ○ transdermal ○ injectable

 • Progestogen-only hormone contraception associated with inhibition of ovulation^b 
 ○ oral ○ injectable

 • Sexual abstinence (Sexual abstinence is considered a highly effective method only if defined as refraining from heterosexual intercourse during the entire period of risk associated with the IP. The reliability of sexual abstinence needs to be evaluated in relation to the duration of the study and the preferred and usual lifestyle of the subject.)

^a Failure rate of < 1% per year when used consistently and correctly. Typical use failure rates differ from those when used consistently and correctly.

^b If locally required, in accordance with Clinical Trial Facilitation Group (CTFG) guidelines, acceptable contraceptive methods are limited to those which inhibit ovulation as the primary mode of action.

Note: Periodic abstinence (calendar, symptothermal, post-ovulation methods), withdrawal (coitus interruptus), spermicides only, and lactational amenorrhoea method (LAM) are not acceptable methods of contraception for this study. Male condom and female condom should not be used together (due to risk of failure with friction).

Collection of Pregnancy Information

Female Subjects who become pregnant

- The Investigator will collect pregnancy information on any female subject who becomes pregnant while participating in this study. Information will be recorded on the appropriate form and submitted to the Sponsor within 24 hours of learning of a subject's pregnancy.
- The subject will be followed to determine the outcome of the pregnancy. The Investigator will collect follow-up information on the subject and the neonate and the information will be forwarded to the Sponsor. The subject will be followed until birth or termination of pregnancy. Any termination of pregnancy will be reported, regardless of fetal status (presence or absence of anomalies) or indication for the procedure.
- While pregnancy itself is not considered to be an AE or SAE, any pregnancy complication or elective termination of a pregnancy will be reported as an AE or SAE. A spontaneous abortion is always considered to be an SAE and will be reported as such. Any post-study pregnancy related SAE considered reasonably related to the IP by the Investigator will be reported to the Sponsor as described in [Section 10.3.5](#). While the Investigator is not obligated to actively seek this information in former study subjects, he or she may learn of an SAE through spontaneous reporting.
- Any female subject who becomes pregnant while participating in the study will discontinue IP or be withdrawn from the study.

10.5. Appendix 5: Genetics

Use and Analysis of DNA

- Genetic variation may impact a subject's response to IP, susceptibility to, and severity and progression of disease. Variable response to IP may be due to genetic determinants that impact drug absorption, distribution, metabolism, and excretion; mechanism of action of the drug; disease etiology; and/or molecular subtype of the disease being treated. Therefore, where local regulations and IRB/IEC allow, a biosample will be collected for DNA analysis from consenting subjects.
- Samples may be used for research related to GB001 and/or asthma and related diseases. They may also be used to develop tests/assays including diagnostic tests related to GB001 and DP2 inhibitors and atopic disease. Genetic research may consist of the analysis of prespecified candidate polymorphisms.
- Samples may be analyzed for variation in candidate genes which dramatically affect the pharmacokinetics of GB001, the safety, and/or efficacy profile. Often times, a large variability in the plasma concentration–time profiles of any medicine can be linked to loss of function mutations in the drug metabolizing enzymes and/or transporters. For example, substantial efforts have been made in reducing the risk of drug–drug interactions related to cytochrome P450 enzymes and variability caused by polymorphic expression of cytochrome P450 enzymes (eg, CYP2D6). The effects of single nucleotide polymorphisms on the PK of GB001 uncovered in the course of this study may help guide future clinical studies and regulatory review of GB001. Additional pharmacogenetic analyses may be conducted if it is hypothesized that doing so may help resolve issues with the clinical data, eg, safety and/or efficacy observations during the life of the study.
- The samples may be analyzed as part of a multi-study assessment of genetic factors involved in the response to GB001 of this class to understand study disease or related atopic conditions.
- The results of genetic analyses may be reported in the CSR or in a separate study summary.
- The Sponsor will store the DNA samples in a secure storage space with adequate measures to protect confidentiality.
- The samples will be retained while research on GB001 continues but no longer than 8 years or other period as per local requirements.

The following genetic parameters may be evaluated in this study:

- Genetics (DNA):

SNPs in a) drug metabolizing and enzymes, b) DP₂ pathway genes, c) asthma & atopic pathway genes, e.g. vitamin D

10.6. Appendix 6: Liver Safety - Actions and Follow-up Assessments

Liver chemistry will be evaluated as specified in the SoA (Section 1.3) and Appendix 2 (Section 10.2). Parameters will include ALT, AST, GGT, bilirubin, total bile acids, and ALP.

For subjects with ALT or AST $> 1 \times \text{ULN}$ and $< 3 \times \text{ULN}$ or total bilirubin or direct bilirubin $> 1 \times \text{ULN}$ and $\leq 1.5 \times \text{ULN}$, confirm the value within 24 to 48 hours. Contact the Medical Monitor to determine the appropriate liver monitoring schedule (eg, weekly or twice a week).

The criteria requiring additional liver monitoring with possible interruption of study intervention are detailed in Table 4.

Table 4: Liver Chemistry Criteria Requiring Additional Monitoring with Possible Interruption of Investigational Product

Criterion	Actions

ALT or AST $\geq 3 \times \text{ULN}$ and $< 5 \times \text{ULN}$ or total bilirubin or direct bilirubin $> 1.5 \times \text{ULN}$ without symptoms believed to be related to liver injury or hypersensitivity, and who can be monitored weekly for 4 weeks
	
 • Notify the Medical Monitor within 24 hours of learning of the abnormality to discuss subject safety. “Additional Liver Panel” in Table 5 may be requested by the Medical Monitor • Confirm values within 24 to 48 hours via repeat labs. If unable to obtain repeat labs within 48 hours, discontinue IP. • Decision to continue or interrupt study intervention will be determined by the Investigator and the Medical Monitor • Subject must return weekly or more frequently for repeat liver chemistry tests (ALT, AST, GGT, ALP, total bile acids, and bilirubin) until the abnormalities resolve, stabilize or return to baseline. • If at any time the subject meets liver chemistry interruption criteria (as specified in Table 5), then follow the instructions in “Actions and Follow-up Assessments” in Table 5 and in consultation with the Medical Monitor initiate relevant assessment procedures

In the case of AEs of interest (Section 10.3.3), potential re-challenge will be restricted to potential DILI cases that have been assessed as unlikely or not related to IP by the HAC and after liver enzymes have returned to baseline levels. When re-challenging with IP, obtain repeat liver chemistries twice weekly in the first 2 weeks and then weekly for 6 weeks after the re-challenge. If there is a rise in liver enzymes $> 2 \times \text{ULN}$, then IP should be discontinued permanently. The criteria requiring interruption of IP with additional liver monitoring is detailed in Table 5.

Table 5: Liver Chemistry Criteria Requiring Investigational Product Interruption and Additional Monitoring

Liver Chemistry – IP Interruption Criteria	
ALT/AST (single occurrence)	ALT or AST \geq 5x ULN
ALT/AST	ALT or AST \geq 3x ULN persists for \geq 4 weeks
+ Bilirubin^{a,b}	ALT or AST \geq 3x ULN and bilirubin > 2x ULN (> 35% direct bilirubin)
+ INR^b	ALT or AST \geq 3x ULN and international normalized ratio (INR) > 1.5, if INR measured
+ Cannot Monitor	ALT or AST \geq 3x ULN and cannot be monitored weekly for 4 weeks
+ Symptomatic^c	ALT or AST \geq 3x ULN associated with symptoms (new or worsening) believed to be related to liver injury or hypersensitivity
Actions and Follow-up Assessments	
Actions	Follow-Up Assessments

 • Immediately discontinue IP • Report the event to the Medical Monitor within 24 hours • Complete the liver event eCRF and complete an SAE data collection tool if the event also met the criteria for an SAE^b • Perform liver chemistry follow-up assessments • Monitor the subject until liver chemistry test abnormalities resolve, stabilize, or return to baseline (see MONITORING) • Do not restart/rechallenge subject with IP unless Medical Monitor approval is granted • If restart/rechallenge not granted, permanently discontinue IP and continue subject in the study for any protocol specified follow up assessments 
MONITORING:
 
 • Repeat liver chemistry tests (include ALT, AST, GGT, alkaline phosphatase, total bile acids, bilirubin, and INR) and perform liver event follow-up assessments within 24 hours • Monitor subject twice weekly until liver chemistry test abnormalities resolve, stabilize, or return to baseline • A specialist or hepatology consultation is recommended 	
Additional Liver Panel
 
 • Viral hepatitis serology^d • Obtain INR and recheck with each liver chemistry assessment until the ALT and/or AST values show downward trend • Obtain blood sample for pharmacokinetic (PK) analysis • Serum creatine phosphokinase (CPK) and lactate dehydrogenase (LDH) • Fractionate bilirubin, if total bilirubin > 2x ULN • Obtain complete blood count with differential to assess eosinophilia • Record the appearance or worsening of clinical symptoms of liver injury, or hypersensitivity, on the adverse event (AE) report form • Record use of concomitant medications (including acetaminophen, herbal remedies, and other over-the-counter medications) on the concomitant medications eCRF • Record alcohol use on the liver event alcohol intake eCRF • Anti-nuclear antibody, anti-smooth muscle antibody, Type 1 anti-liver kidney microsomal antibodies, and quantitative total immunoglobulin G (IgG) or gamma globulins • Serum acetaminophen assay • Liver imaging (ultrasound, magnetic resonance, or computerized tomography) and/or liver biopsy to evaluate liver disease

^a Serum bilirubin fractionation should be performed if testing is available. If serum bilirubin fractionation is not immediately available, discontinue IP if ALT or AST \geq 3x ULN **and** bilirubin > 2x ULN. Additionally, if serum

bilirubin fractionation testing is unavailable, **record the absence/presence of detectable urinary bilirubin on dipstick** which is indicative of direct bilirubin elevations suggesting liver injury.

^b All events of ALT or AST $\geq 3x$ ULN **and** bilirubin $> 2x$ ULN ($> 35\%$ direct bilirubin) or ALT or AST $\geq 3x$ ULN **and** INR > 1.5 may indicate severe liver injury (**possible ‘Hy’s Law’**) **and must be reported as an SAE (excluding studies of hepatic impairment or cirrhosis)**. The INR stated threshold value will not apply to subjects receiving anticoagulants. INR is not part of routine laboratory assessments in this study.

^c New or worsening symptoms believed to be related to liver injury (such as fatigue, nausea, vomiting, right upper quadrant pain or tenderness, or jaundice) or hypersensitivity (such as fever, rash or eosinophilia).

^d Includes: expanded viral hepatitis serology ([Table 3](#)).

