10.2. Appendix 2: Clinical Laboratory Tests

The tests detailed in [Table 2](#) and [Table 3](#) will be performed by the central laboratory.

Protocol-specific requirements for inclusion or exclusion of subjects are detailed in [Section 5](#) of the protocol.

Additional tests may be performed at any time during the study as determined necessary by the Investigator or required by local regulations.

Investigators must document their review of each laboratory safety report in subject's source records.

Table 2: Protocol-Required Safety Laboratory Assessments

Hematology	
White blood cell count (WBC) with differential (neutrophils, lymphocytes, monocytes, eosinophils, basophils)	Red blood cell (RBC) with indices (MCV and MCH)
Hemoglobin	Hematocrit
Platelet count	
Clinical Chemistry	
Alanine aminotransferase (ALT)	Aspartate aminotransferase (AST)
Alkaline phosphatase ¹	Gamma-glutamyl transferase (GGT)
Total and direct bilirubin (fractionated)	Albumin
Calcium	Blood urea nitrogen (BUN)
Sodium	Creatinine
Chloride	Potassium
Glucose (non-fasting)	Lactic dehydrogenase (LDH)
Uric acid	Magnesium
Total protein	Total bile acid
Coagulation	
INR	
Urinalysis	
Basic urinalysis (dipstick) to be performed at the Screening visit, Week 24, and Early Discontinuation of IP/Withdrawal from Study visits. Reflex microscopic evaluation will be performed if the dipstick is abnormal.	

Other Laboratory Assessments

• Human chorionic gonadotropin (hCG) pregnancy test (as needed for women of childbearing potential)• Follicle-stimulating hormone and estradiol (as needed in women of non-childbearing potential only)• Viral hepatitis serology (hepatitis B surface antigen [HBsAg], and hepatitis C virus antibody)• Urine cotinine

¹Fractionation of ALP if ALP > 1xULN.

The additional tests listed in [Table 3](#) will be collected only as part of liver safety actions and follow up. See also Appendix 6 ([Section 10.6](#)).

Table 3: Liver Safety Laboratory Assessments

Hematology

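### Appendix 6 leaves out subjects with bilirubin above 1.5x ULN and ALT/AST below 3x ULN who have liver symptoms or cannot attend weekly: they lose the Table 4 actions and meet no Table 5 stop rule

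*Protocol*

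**What the plan says.** Protocol Appendix 6 (Section 10.6) sets three tiers of action.

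- **Lead paragraph.** It applies when ALT or AST is above 1x and below 3x ULN, or when total or direct bilirubin is above 1x and at most 1.5x ULN. The site must "confirm the value within 24 to 48 hours. Contact the Medical Monitor to determine the appropriate liver monitoring schedule".
- **Table 4.** It applies when ALT or AST is at least 3x and below 5x ULN, or total or direct bilirubin is above 1.5x ULN, in subjects "without symptoms believed to be related to liver injury or hypersensitivity, and who can be monitored weekly for 4 weeks". The Medical Monitor is told within 24 hours, values are confirmed within 24 to 48 hours, and liver tests follow at least weekly. There is also a conditional stop: "If unable to obtain repeat labs within 48 hours, discontinue IP".
- **Table 5.** There are six rows. One needs ALT or AST of at least 5x ULN and the other five need at least 3x ULN. Two of those five add a clinical condition: "associated with symptoms (new or worsening) believed to be related to liver injury or hypersensitivity", or "and cannot be monitored weekly for 4 weeks". The first action is to stop IP at once.

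Table 5 footnote c describes the symptoms meant: "New or worsening symptoms believed to be related to liver injury (such as fatigue, nausea, vomiting, right upper quadrant pain or tenderness, or jaundice". Appendix 2, Table 2 lists "Total and direct bilirubin (fractionated", so both bilirubin measures are available to the site.

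**The concern.** Symptoms and inability to attend weekly should raise the required response. On the ALT/AST route they do, by moving the subject from Table 4 to Table 5. On the bilirubin route they take the subject out of Table 4, and no Table 5 row is open. A jaundiced subject is then owed less than one with the same bilirubin and no symptoms.

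Section 2.3.1 names drug-induced liver injury as a potential risk and reports two Hy's Law cases, one of them in this study and still blinded. Footnote a to Table 5 itself treats detectable urinary bilirubin as "indicative of direct bilirubin elevations suggesting liver injury". Randomization criterion 8 (Section 5.3) required screening bilirubin below 1x ULN, so a total bilirubin above 1.5x ULN is a change since screening. Being unable to attend weekly is also realistic, because Appendix 12 plans for visits missed during the pandemic.

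Section 10.3.3 points the same way. It lists raised blood bilirubin, alone or with other conditions, as an adverse event (AE) of interest when it leads to a Table 5 discontinuation. No Table 5 row can be met on bilirubin without ALT or AST of at least 3x ULN.

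**Working it through.** The plan gives no figure to reproduce, so the check is of the rules themselves.

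**1. Rules as conditions** (A = higher of ALT and AST; T, D = total and direct bilirubin; all in multiples of ULN)

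- Lead paragraph: 1 < A < 3, or 1 < T ≤ 1.5, or 1 < D ≤ 1.5.
- Table 4: (3 ≤ A < 5, or T > 1.5, or D > 1.5), and no symptoms, and weekly monitoring possible.
- Table 5: A ≥ 5; or A ≥ 3 together with any one of: persistence for at least 4 weeks, bilirubin > 2, INR > 1.5, weekly monitoring impossible, symptoms.

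**2. Enumeration.** Take A at 0.8 or 2, bilirubin at 1.8 or 2.5 (one value for both measures), symptoms yes/no, and weekly monitoring yes/no: 2 × 2 × 2 × 2 = 16 combinations.

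- No symptoms and monitorable: 2 × 2 = 4, all in Table 4.
- Symptoms, no weekly monitoring, or both: 16 − 4 = 12, none in Table 4 or Table 5.
- Of those 12, the 6 with A = 2 reach the lead paragraph only. The 6 with A = 0.8 reach no tier.

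For comparison, take A = 3.5 with bilirubin at 0.8. The 3 combinations with symptoms and/or no weekly monitoring all meet Table 5, and IP stops. The enumeration tests the logic and says nothing about frequency.

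**3. Total and direct bilirubin taken separately.** Subject able to attend weekly:

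| ALT/AST | Total / direct bilirubin | With symptoms | Without symptoms |
|---|---|---|---|
| 0.9x | 1.4x / 1.4x | Lead paragraph | Lead paragraph |
| 0.9x | 1.8x / 1.3x | Lead paragraph only | Table 4 |
| 0.9x | 1.8x / 0.9x | No tier | Table 4 |
| 0.9x | 1.8x / 1.8x | No tier | Table 4 |
| 2.0x | 1.8x / 1.8x | Lead paragraph only | Table 4 |
| 3.5x | normal | Table 5, IP stopped | Table 4 |

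Rows one and four show a second reversal. With symptoms and normal ALT/AST, the required action falls as both bilirubin measures rise from 1.4x to 1.8x ULN.

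**4. Alternative reading.** The result is the same whether Table 4's two conditions qualify both routes or the bilirubin route only. It would change only if they qualified ALT/AST alone. The wording does not support that, since they directly follow the bilirubin criterion.

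**5. Time to the next scheduled test.** Section 1.3 places liver chemistry at Weeks 0, 1, 2, 3, 4, 8, 12, 16, 20 and 24. After Week 4 the gap is 4 × 7 = 28 days, or 28 + 2 + 2 = 32 with the ±2-day windows. Table 4 allows at most 7 days. The 28 to 32 days is a worst case in which nobody orders an unscheduled test.

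**The case against.** The literal reading is hard to dispute; the argument is about consequence.

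- **General duties.** Suspected liver injury triggers the low threshold for stopping IP in Section 2.3.1. Section 8 calls for immediate discussion of safety concerns with the Sponsor, which for a symptomatic subject does much of the work of the 24-hour notice. Section 8.2.4 requires clinically significant results to be repeated, Section 8.3.3 requires liver events to be followed, and Section 10.3.4 obliges the Investigator to arrange further tests as medically indicated or as the Sponsor requests. Section 4.1.2 allows unscheduled visits for this. The 28 to 32 day gap would arise only if these duties were neglected.
- **Few subjects.** Known liver and biliary disorders, including Gilbert's syndrome, are excluded, and the possible Hy's Law pattern is in Table 5.
- **Design choice.** Even in Table 4, isolated bilirubin elevation does not by itself stop IP; the Investigator and Medical Monitor decide. Tying the Table 5 stops to ALT/AST may be deliberate.
- **Hidden text.** Section 6.2.5, on the unblinded Sponsor Medical Monitor, and a block after Section 8.3.6 are redacted. The remit of the Hepatology Assessment Committee is not visible.
- **Cost.** Amendment 3, which also changed these liver rules, was classed as substantial. The study runs in 11 countries, and the SAP put the last subject's completion about 4 to 5 months after April 2020.

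Most of this stands as a limit on size. None of the visible general provisions sets a repeat-lab deadline, an automatic stop or a test interval. A deliberate choice to tie stops to ALT/AST would not explain why symptoms remove the Table 4 actions as well.

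**Conclusion.** The gap is real and should be fixed. With bilirubin above 1.5x ULN and ALT/AST below 3x ULN, liver or hypersensitivity symptoms or no weekly monitoring remove the Table 4 actions and trigger nothing in Table 5. The lead paragraph gives partial cover, and its Medical Monitor contact may lead to weekly or twice-weekly tests. Where it does not apply, no visible Appendix 6 tier does.

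The number of subjects is unknown and probably small, and efficacy conclusions are unaffected. The conclusion rests on the visible text of Appendix 6, which is readable in full for both tables. Redacted sections might reduce the practical shortfall, but that could not be checked.

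**What to change.** 1. **Symptomatic subjects.** Remove the no-symptoms condition from Table 4's bilirubin criterion, so that Table 4 becomes the minimum response. Alternatively, add a Table 5 row for total or direct bilirubin above 1.5x ULN with symptoms.
2. **Subjects who cannot attend weekly.** Add a Table 5 row for bilirubin above 1.5x ULN when weekly monitoring is not possible, so that IP stops as on the ALT/AST route. Table 4 cannot serve these subjects because they could not keep its weekly visits.

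The drafting is one or two table lines and uses tests already in Appendix 6. The operational cost is a few more repeat tests or IP interruptions; benign triggers should be few, given the eligibility limits. A new symptomatic Table 5 row would make those events AEs of interest under Section 10.3.3, with mandatory follow-up labs. A cannot-monitor row would not, because that section excepts such events. A new stop rule may need a full amendment with ethics approval rather than a clarification letter. Deleting the symptom condition from Table 4 is the lighter change if only one can be made quickly, but it leaves the cannot-monitor gap open.
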